### 11.2.4 Baseline rSO2 Data Acquisition

Once in the operating room the patient will have standard monitors applied as well as bilateral rSO2 sensor pads to the glabrous skin of the forehead just above the eyebrow line. The application of the pads will be preceded by swabbing the skin with an alcohol pad and applying both mastisol and clear tape to promote pad adhesion throughout the collection of NIRS data.

#### 11.2.4.1 Room Air Baseline rSO2

Once the pads are in place approximately one minute will elapse to insure that a reliable NIRS signal is obtained and that it is producing stable values bilaterally while they are in the supine position just prior to the preoxygenation period of anesthesia induction. Both the left and right baseline values will then be recorded. The time of this event will be recorded on the study data collection tool.

#### 11.2.4.2 Oxygen Supplemented Baseline rSO2

Once that subject has been breathing 100% oxygen for a full two minutes as assessed by the research assistant's timer the oxygen supplemented rSO2 baselines will be recorded when the NIRS data is stable bilaterally. The time of this event will be recorded on the study data collection tool.

11.2.4.3 Blinding of Control Group

After recording the two sets of baseline rSO2 data the subjects that have been randomized to the control group will have their rSO2 data electronically blinded via activation of a device modification that will have been previously performed by the device manufacturer.

### 11.3 Protocol Assessments and Procedures – Intraoperative and Immediate Postoperative Period

#### 11.3.1 General Intraoperative and Immediate Postoperative Period Description

During this period a host of clinical variables will be collected on each subject that will serve as the primary endpoints of this pilot study.

#### 11.3.2 Serial rSO2, SpO2 and Blood Pressure Data Collection

Anesthesia induction will be accompanied by continuous electronic acquisition of the rSO2, SpO2 and MAP data. PICIS will be used to collect blood pressure data as well as rSO2 data in individuals randomized to the intervention group. The INVOS devices will also be collecting the rSO2 data in both groups of subjects for download at a later time. Note that the time on the oximeter will be synchronized with the time on the PICIS Anesthesia Computer prior to the collection of any NIRS or hemodynamic data.

#### 11.3.3 Intraoperative and Immediate Postoperative Clinical Variable Data Collection

##### 11.3.3.1 Intraoperative Clinical Variables Collected

Vasopressor use  
Inotrope use

Amount of narcotic administered  
Time on single lung ventilation

Urine output	Anti-emetic medication administered
Myocardial ischemia	Total crystalloid administered
Stroke or TIA	Total colloid administered
Hyperglycemia $AUC_{Glu} > 110$	Total transfused allogeneic RBCs
Atrial fibrillation	Atrial fibrillation
Use of epidural catheter	
Surgical procedure	$rSO_2$ prompted change in surgery
Time spent in operating room	

#### 11.3.3.2 Immediate Postoperative Clinical Variables Collected

Vasopressor use	Antiemetic medication administered
Inotrope use	Total crystalloid administered
Urine output	Total colloid administered
Myocardial ischemia	Temperature on arrival
Stroke or TIA	Aldrete score (arrival, 30 & 60 min)
Hyperglycemia $AUC_{Glu} > 110$	PONV Severity
Atrial fibrillation	Time to PACU d/c readiness
Time spent in PACU/ICU	Time on mechanical ventilation
Amount of narcotic administered	

### 11.4 Protocol Assessments and Procedures – Postoperative Follow Up Period

#### 11.4.1 General Description Postoperative Follow Up Period

During this period each subject will undergo repeat neuropsychological testing and a host of postoperative clinical variables will be collected prior to their discharge from the hospital. Additionally, this period includes a 4 week postoperative follow up telephone interview with each subject.

#### 11.4.2 Postoperative Day 1 and 3 MMSE and CAM Assessments

The MMSE and the CAM assessment will be repeated on each subject on postoperative days 1 and 3.

#### 11.4.3 Postoperative Clinical Variables Collected

##### 11.4.3.1 Postoperative Clinical Variables Collected

ICU-LOS	Atrial fibrillation
Hospital-LOS	SNF or Rehab transfer on d/c

Time spent in SNF/Rehab	Postoperative myocardial ischemia
Need for hospital readmission	Postoperative RBC transfusion
Change in baseline renal function	Any postoperative infection
Return of bowel function time	Postoperative composite endpoint
Postoperative stroke or TIA	

#### 11.4.4 Postoperative 4 Week Telephone Interview

At 4 weeks (+/- 5 days) from the day of the surgical procedure a study team member will make a telephone call to the subject with the goal of assessing overall well being, if there was any need for hospital readmission or emergency ward visit, and if applicable how many days the subject remained in a skilled nursing facility or rehabilitation hospital.

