- 4) Assess the interventional cohort's preoperative demographics and collected covariates for association with the ease or difficulty of mitigating observed cerebral desaturation events.

Exploratory analyses will include performing all possible comparisons of the two groups based upon all collected perioperative variables to examine the potentially significant relationships between the collected clinical variables representing surrogates of organ perfusion/function and cerebral oximetry desaturations (AUCrSO2). The following exploratory endpoints will be assessed:

- Logistic regression analysis to determine the most relevant AUCrSO2 desaturation value(s) associated with any detrimental clinical outcome(s) monitored in this study
- Logistic regression analysis to determine the most relevant AUC blood pressure values associated with any detrimental clinical outcome(s) monitored in this study
- Comparison of baseline rSO2 values (room air and oxygen supplemented) to all collected clinical variables to assess for possibly significant associations
- Explore the potential impact of rSO2 monitoring on changing the surgical conduct of the procedure

**Methodology:** Single center, prospective, randomized, controlled clinical pilot study

**Number of Subjects:** 100 subjects with balanced randomization (1:1) to control (blinded NIRS data) or intervention (open NIRS data) cohorts

**Main Criteria for Inclusion:** Elderly patients (> 65 years of age) scheduled for a thoracic surgical procedure at UHCMC that will involve SLV.

**Duration of Treatment:** Cerebral oximetry monitoring will begin with an assessment of both room air and oxygen supplemented bi-frontal baseline NIRS values and continue through the surgery to either PACU discharge or the initial 12 hours of post surgical ICU treatment. Mini Mental Status exam testing and Delirium testing with the Confusion Assessment Method will occur preoperatively and postoperatively through post-operative day (POD) #3 (or discharge if that occurs sooner than POD #3).

Enrolled subjects will be followed during the index hospitalization and will undergo a 30 day follow up telephone interview to assess their progress following hospital discharge.

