### 7.2.4 Postoperative Follow Up Period

The postoperative follow up period will continue from PACU or ICU discharge until the patient telephone interview 4 weeks after the surgical procedure. The active elements of the study protocol which involve direct subject interaction during this period include a postoperative day 1 and 3 MMSE and CAM delirium assessments as well as the 4 week post-procedure follow up telephone interview to assess the patient's general state of health following surgery including a query of any need for hospital readmission.

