$AUC_{SpO_2} < 75\%$  regardless of intraoperative  $FiO_2$  values

$AUC_{SpO_2} < 70\%$  regardless of intraoperative  $FiO_2$  values

- Time from procedure completion to arrival in the post anesthesia care unit (PACU) or ICU
- Temperature upon PACU/ICU arrival
- Aldrete score upon PACU/ICU arrival and at 30 & 60 (or at discharge) min post-PACU arrival (See Appendix A)
- Any occurrence of immediate postoperative atrial fibrillation
- Any myocardial ischemia in the immediate postoperative period
- Any need for allogeneic RBC transfusion in the immediate postoperative period
- Any observed stroke or TIA in the immediate postoperative period
- Time to clinical readiness for PACU discharge as assessed by established institutional discharge criteria (see Appendix B)
- Frequency and severity of nausea and vomiting observed in the PACU and/or ICU as assessed by an accepted postoperative nausea and vomiting scale
- ICU length of stay (ICU-LOS) [anticipated to be at least 10-20 evaluable subjects for this parameter if 100 patients are enrolled] which will be defined as time to clinical readiness for ICU discharge as assessed by the clinical team caring for the patient
- Postoperative mechanical ventilation time if still intubated and admitted to the ICU following the surgical procedure
- Use of any immediate postoperative, intravenous vasopressor and/or inotropic agent (as assessed by amount of time in minutes on any IV drug support regardless of dose and assessed by total dose of drug delivered to patient)
- Immediate postoperative urine output in any patient with an indwelling foley catheter as assessed by mLs urine/kg/hr for total time in operating room
- Hospital length of stay (H-LOS)
- Need for skilled nursing facility/rehabilitation hospital admission upon discharge from index hospitalization
- Length of time spent in a skilled nursing facility/rehabilitation hospital upon discharge from index hospitalization if a relevant data point for each subject

- Need for hospital readmission for any reason within 30 days of surgical procedure
  - Observed change from preoperative baseline Mini-mental Status Examination (MMSE) score (including postoperative day #1 and postoperative day #3 or discharge scores)
  - Presence/absence of postoperative delirium (as assessed by the CAM Delirium assessment tool results obtained preoperatively and postoperatively upon PACU discharge, Day#1 and 3 [or hospital discharge])

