### 9.1.1 Inclusion Criteria:

1. Any male or female patient  $\geq 65$  years of age and able to provide informed consent (or consent may be provided by a legally authorized representative) who is scheduled for a thoracic surgical procedure that is expected to involve the use of intraoperative single lung ventilation (SLV)
2. Able to adequately complete a baseline mini-mental status examination (MMSE)

3. Able to complete a baseline confusion assessment method (CAM) examination
4. Able to obtain bi-frontal baseline rSO2 values prior to induction of anesthesia

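### The only source described for 30-day readmission is one telephone call to the subject between day 23 and day 33, so some readmissions may go uncounted

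*Combined protocol and SAP*

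**What the plan says.** Section 7.4.1.2, under the Primary Endpoints heading, lists "Need for hospital readmission for any reason within 30 days of surgical procedure". Section 7.2.4 describes the contact after discharge as a 4-week telephone interview, "including a query of any need for hospital readmission". Section 11.4.4 sets the timing ("At 4 weeks (+/- 5 days) from the day of the surgical procedure a study team member will make a telephone call") and the content: "telephone call to the subject with the goal of assessing overall well being, if there was any need for hospital readmission or emergency ward visit". It also asks, where relevant, about days spent in a nursing or rehabilitation facility. The synopsis describes the same contact differently: subjects "will undergo a 30 day follow up telephone interview to assess their progress following hospital discharge".

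No other section supplies a second described source:

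- Section 11.4.3.1 lists readmission as a collected variable but names no source. Section 11.4.1 says that "a host of postoperative clinical variables will be collected prior to their discharge from the hospital", with the telephone interview as an addition.
- Review of patient records is described only in Section 11.1.3, for preoperative variables.
- Table 1 marks adverse event monitoring for the follow-up period. Section 13.2 starts a serious adverse event report once the team has learned of the event, without saying how it would learn of one after discharge. Section 13.1.2 does not list hospitalization as a criterion.
- No proxy informant, repeat call, post-discharge record check, or rule for non-contact or death is described. Section 15 has no missing-data rule.

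**The concern.** There are two separate weaknesses. First, the endpoint window closes at day 30, but the call may be made up to a week earlier. Second, the informant is the subject. The trial enrols people aged 65 and over, Section 9.1.1 says that "consent may be provided by a legally authorized representative", and dementia is among the recorded covariates. Being dead, in hospital or impaired on the day of the call makes an answer less likely or less accurate. Those states are plausibly related to readmission and to outcomes the intervention is meant to improve, so the loss may be informative.

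The stake is set by Section 6.2: the pilot exists to pick endpoints for a larger trial. If readmission is poorly ascertained, it could be wrongly chosen or dropped, its rate could be set too low in planning, and unequal contact could create or hide a difference between arms.

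**Working it through.** The documents give no readmission rate, contact rate or power calculation, so there is no plan figure to reproduce. Step 1 uses only the documents' figures. Steps 2 to 4 rest on assumed rates.

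**1. Window.** Inputs: 4 weeks = 28 days, plus or minus 5 (Section 11.4.4), and 30 days (Section 7.4.1.2). Unobserved days = max(0, 30 − call day).

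- Call on day 23: 30 − 23 = 7 days; 7/30 = 23%.
- Call on day 28: 30 − 28 = 2 days; 2/30 = 7%.
- Call on day 33: none.

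Of the 11 permitted call days (23 to 33), the 7 from day 23 to day 29 fall before day 30. These are shares of calendar time. They are not shares of events, because the documents say nothing about when readmissions occur.

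**2. Contact and reporting (assumed rates).** Let p be the true readmission rate, cR and cN the probabilities of reaching readmitted and other subjects, and s the probability that a readmission is reported. Per 100 subjects, counted = 100·p·cR·s and reached = 100·p·cR + 100·(1 − p)·cN. Take p = 10% and cN = 95%.

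- cR = 95%, s = 100%: counted 9.5, reached 95.0. Rate among those reached 10.0%; 9.5% if non-contact is scored as no event.
- cR = 80%, s = 100%: counted 8.0, reached 93.5. Rates 8.6% and 8.0%.
- cR = 80%, s = 90%: counted 7.2, reached 93.5. Rates 7.7% and 7.2%.
- cR = 60%, s = 90%: counted 5.4, reached 91.5. Rates 5.9% and 5.4%.

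The share of readmissions counted is cR·s, which does not depend on p. In the last three cases it is 80%, 72% and 54%. In the first case the rate among those reached is unbiased.

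**3. Unequal contact between arms (assumed rates).** Suppose both arms truly have 13% readmission. Everyone is reached in one arm. In the other, 15% are not reached; their risk is 30%, against 10% in those reached: 0.85 × 10% + 0.15 × 30% = 13%. Among those reached, the observed rates are 13% and 10%, a 3-point gap with no true effect. Scoring non-contact as no event gives 13% and 0.85 × 10% = 8.5%.

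**4. Scale.** With 50 per arm, 3 points is 1.5 subjects. The standard error of the difference at 13% in each arm is √(2 × 0.13 × 0.87/50) = 6.7 points. For an assumed 20% v 10%, power (normal approximation, two-sided 0.05) is 29% with full capture, 21% at 72% capture and 17% at 54% capture: low in every case.

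**The case against.** The strongest reply is that silence is not exclusion. A reader might infer that the call is the sole source, but the documents never say so. Table 1 has separate follow-up rows for postoperative variables, adverse events and the telephone interview. Section 7.4.1.2 lists infection up to day 30, which the call's stated questions do not name, so some other source after discharge may be intended (although that item also says to discharge). Some readmissions could qualify as serious adverse events under the medically significant criterion. This stands: the supportable claim is that the call is the only source described.

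A reader might also infer that whole groups are missed and that the endpoint is undercounted as a matter of fact. The documents do not support that:

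- Facility residents are meant to be covered, since the call asks about facility days.
- Section 9.1.1 requires every subject to complete a baseline MMSE and CAM, which limits how impaired subjects are at entry. It does not rule out later decline.
- A death without readmission is a competing event that needs a rule. It is not a missed readmission.
- Section 15 refers to observed clinical data but states no complete-case rule, so it does not follow that subjects not reached drop out.
- Bias from non-contact or misreport requires that contact or reporting depend on readmission status, or that non-contact be scored as no event.

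The unequal-contact example is an extreme choice, and its gap is well inside sampling error. Readmission is also one of dozens of variables in a 100-subject pilot. These points limit the size and severity of the concern. They do not answer the window gap, which follows from the protocol's own figures.

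**Conclusion.** The point holds as a weakness in the described method. For an endpoint listed as primary, the only described source is one call to the subject, and that call may fall up to 7 days (23% of the window) before the endpoint closes. Readmissions may also be lost through non-contact or misreport, and the arms may be affected differently if contact differs by arm. An actual undercount, or actual bias between arms, is not shown. The 54% to 80% range and the 3-point example illustrate assumed rates only, and the true size cannot be derived from the documents. No sample-size figure or decision rule changes. It is worth acting on because the pilot's purpose is to choose and size endpoints for the next trial, and because the remedy costs little.

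**What to change.** In Sections 11.4.4 and 7.4.1.2:

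- Determine readmission and vital status through day 30 for every randomised subject from the study hospital's own record, checked on or after day 30.
- Make or complete the call on or after day 30, and use it to add events at other hospitals. Reconcile the synopsis (30 days) with Sections 7.2.4 and 11.4.4 (4 weeks).
- Where the subject cannot be reached or cannot answer, put the same questions to the representative, family or facility, and record who answered.
- Keep the endpoint as readmission. Report deaths before day 30 beside it by arm, with readmission-or-death as a supporting analysis.
- State that non-contact is not counted as no event, and report the number not reached by arm.

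The cost is one record look-up per subject at a single centre, a proxy contact on the case report form and a little coordinator time. The drawback is that proxy reports are less detailed.

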### 12 TRIAL SAFETY

#### 12.1 Expert Clinician Unbiased Trial Safety Assessment

This trial will not employ a data safety monitoring board as three clinical trials with a similar design, sicker patients and larger (n) values have been previously conducted using the same cerebral oximetry device without evidence of safety concerns. (Ref Casati, Murkin, Slater) Instead, there will be two planned interim assessments of the collected adverse event data that will be reviewed by a clinical expert in the care of thoracic surgical patients as well as in clinical trial design and execution. [name], M.D. of the Department of Anesthesiology at Duke University School of Medicine will perform a review of collected adverse event data after enrollment of 25 subjects and 50 subjects. If [name] has concerns additional analyses will be performed on the collected clinical data to determine if any real safety issues exist for the subjects participating in this trial. [name] will provide a report to detail his conclusions and recommendations based upon the data he reviews. This data will be shared with the UHCMC IRB.

### 13 ADVERSE EVENTS

#### 13.1 DEFINITIONS

##### 13.1.1 Adverse Event

An adverse event (AE) is defined as any untoward medical occurrence in a patient or clinical investigation subject administered a medicinal product or procedure and which does not necessarily have a causal relationship with this treatment. An AE can therefore be any unfavorable and unintended sign (including an abnormal lab finding), symptom or disease temporarily associated with the use of a medicinal product or procedure, whether or not considered related to this treatment.

---

Planned hospital admissions and/or surgical operations for an illness or disease that existed before the drug or procedure was given to the subject or the subject was randomized in a clinical study are not to be considered AEs.

The severity of an AE and the relationship to study drug will be assessed by the investigator. The investigator will ensure that any patient experiencing an AE receives appropriate medical support until the event resolves.

### 13.1.2 Serious Adverse Events

A serious adverse event (SAE) is any untoward medical occurrence that:

- results in death,
- is life threatening, i.e., the subject was,, in the opinion of the investigator, at immediate risk of death from the event as it occurred (It does not include an event that, had it occurred in a more severe form, might have caused death),
- results in a persistent or significant disability/incapacity, is a congenital anomaly/birth defect, or
- is another medically significant event that, based upon appropriate medical judgment, may jeopardize the subject and may require medical or surgical intervention to prevent one of the outcomes listed above

A distinction should be drawn between serious and severe AEs. Severity is an estimate or measure of the intensity of an AE, while the criteria for serious AEs are indications of adverse subject outcomes for regulatory reporting purposes. A severe AE need not necessarily be considered serious and a serious AE need not be considered severe.

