### **6.3 Secondary Objectives**

Secondary objectives of this pilot study include the following:

- 1) Assess the frequency of cerebral desaturations in both the intervention and control cohorts by examining both the total number of patients experiencing any cerebral desaturation as well as the total number of events among patients experiencing any cerebral desaturation (of at least 5% below baseline and progressively larger desaturations). These analyses will be conducted on the entire study population as well as upon each cohort. The Area Under the Curve (AUC) analysis

technique [incremental desaturation categories will be assessed based upon 5 to 50% decreases, measured in 5% increments, from established room air baseline as well as oxygen supplemented pre-incision baselines as well as desaturations below absolute measured rSO2 values] will be employed to conduct these analyses.

- 2) Assess the frequency of adverse clinical events and serious adverse events overall and in each cohort.
- 3) Perform a comprehensive assessment of the frequency and efficacy of predefined rSO2 desaturation mitigation interventions and their collective ability to affect the observed cerebral oximetry values.
- 4) Assess the interventional cohort's preoperative demographics and collected covariates for association with the ease or difficulty of mitigating observed cerebral desaturation events.

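### The SAE definition has no criterion for unplanned or prolonged hospitalisation, so non-life-threatening readmissions count as SAEs only at discretion and the SAE frequency can be understated

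*Combined protocol and SAP*

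**What the plan says.** Section 13.1.2 gives the whole SAE definition. An event is serious if it "results in death", if the subject was "at immediate risk of death from the event as it occurred", or under the next bullet, which reads "results in a persistent or significant disability/incapacity, is a congenital anomaly/birth defect, or". The final criterion is a catch-all: "is another medically significant event that, based upon appropriate medical judgment, may jeopardize the subject and may require medical or surgical intervention to prevent". What is to be prevented there is any outcome higher up in the list. The life-threat criterion excludes events that could have been fatal only in a worse form.

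Section 13.1.1 deals with hospital admission once, as an exemption from AE status: "Planned hospital admissions and/or surgical operations for an illness or disease that existed before the drug or procedure was given to the subject". Unplanned admissions are not exempted.

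Section 7.4.1.2 lists as an endpoint "Need for hospital readmission for any reason within 30 days of surgical procedure", and also hospital length of stay. Section 11.4.4 has staff ask about readmission at the telephone call, 4 weeks plus or minus 5 days after surgery. Table 1 in Section 11 runs AE and SAE monitoring through the postoperative follow-up period.

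Section 6.3, item 2, sets the safety objective: "Assess the frequency of adverse clinical events and serious adverse events overall and in each cohort". Section 13.2 requires SAE reports within 24-48 hours of learning of the event and shares them with the IRB. Ordinary AE reports are kept with the study records and go to the external expert at the reviews set in Section 12.1, after 25 and after 50 subjects are enrolled.

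**The concern.** The protocol collects readmissions and treats unplanned ones as possible adverse events, but has no rule that makes them serious. In subjects aged 65 or over having thoracic surgery, a readmission for a complication is an event that a reader of the SAE table would expect to find there. Under the written definition it may or may not appear, according to how one person reads the last criterion.

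Two things are at stake. The first is the SAE comparison between cohorts, which needs a rule that two investigators would apply alike. The second is prompt reporting: SAE status alone triggers the 24-48 hour report and the individual report to the IRB. The trial has no data safety monitoring board, and Section 12.1 schedules no expert review after the one at 50 subjects. For an event that arises later, the SAE report is the only event-level route to outside eyes that the protocol describes.

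**Working it through.** **Text check.** Take a hypothetical 72-year-old readmitted on day 12 with pneumonia, never at immediate risk of death and discharged well.

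| Rule | Result |
|---|---|
| 13.1.1, AE | Untoward and unplanned, so an AE; the planned-admission exemption does not apply |
| 13.1.2, death | Not met |
| 13.1.2, life threat | Not met; a worse form of the event does not count |
| 13.1.2, disability or birth defect | Not met |
| 13.1.2, catch-all | Open: met if someone judges that intervention may be needed to prevent death, disability or another listed outcome |
| 7.4.1.2, readmission endpoint | Counted |
| 13.2, 24-48 hour SAE report shared with the IRB | Only if the catch-all is invoked |

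The same event is therefore certain to be counted as an endpoint and as an AE, and uncertain to be counted as an SAE. A stay prolonged by a non-life-threatening complication follows the same path.

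**Direction.** Adding a criterion can only raise the SAE count or leave it unchanged. Any error from the omission is an undercount.

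**Size.** The documents give no SAE rate and no readmission rate, so there is no figure of the plan's to reproduce. For illustration only:

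- n = 50 per arm, from 100 subjects randomised 1:1 (Section 7.1).
- r = proportion of subjects with an unplanned readmission within 30 days. Assumed 3% to 15%, the same in both arms.
- c = share of those counted as SAEs anyway under an existing criterion, including the catch-all. Assumed 0, 0.5 or 0.8.

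Expected number left out per arm = 50 × r × (1 − c). Chance of at least one among all 100 subjects = 1 − [1 − r(1 − c)]^100.

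| r | c = 0 | c = 0.5 | c = 0.8 |
|---|---|---|---|
| 3% | 1.5 (95%) | 0.75 (78%) | 0.3 (45%) |
| 5% | 2.5 (99%) | 1.25 (92%) | 0.5 (63%) |
| 10% | 5.0 (>99%) | 2.5 (99%) | 1.0 (87%) |
| 15% | 7.5 (>99%) | 3.75 (>99%) | 1.5 (95%) |

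For example, 50 × 0.15 × 1 = 7.5 and 50 × 0.03 × 0.2 = 0.3. The c = 0 column is an upper bound, since it supposes that no readmission meets any other criterion. Prolonged index stays would be additional.

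**Call window.** Four weeks plus or minus 5 days is day 23 to day 33 (28 − 5 and 28 + 5). A call on day 23 leaves 30 − 23 = 7 days of the readmission endpoint's window uncovered.

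**The case against.** The strongest reply is that the catch-all already does the work. It does not require hospitalisation to be a listed outcome. It requires an event that may endanger the subject and may need intervention to prevent a listed outcome, and death and disability are listed. Pneumonia after thoracic surgery could well meet it. This stands, and it means a reader should not infer that readmissions are shut out of the SAE count, or that the count is certainly understated. What remains is that inclusion is discretionary and not fixed by rule.

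The second reply is that little information is lost. This also largely stands. Readmission and hospital length of stay are endpoints, Section 7.4.1.2 also records infections to day 30, and the secondary objective covers AEs as well as SAEs. A reader might infer that the external expert's review is incomplete. The documents do not support that for the two scheduled reviews: Sections 12.1 and 13.2 send the expert AE reports whatever their seriousness, and Section 12.1 says the data go to the IRB.

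A reader might also infer bias between arms, because clinicians and the research assistant see the oximetry readings in the intervention arm (Section 10.3). Classification by judgement could differ by arm, but the documents do not say who decides seriousness or whether that person knows the allocation. No such bias is shown.

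Finally, two criteria run together in one bullet of the text as I have it. Nothing suggests that a hospitalisation line has dropped out.

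**Conclusion.** Wrong as written. The definition is a stated, closed list that leaves the seriousness of ordinary readmissions and complication-prolonged stays to discretion, while the trial collects those same readmissions by a fixed rule. The SAE frequency overall and by cohort can be understated and is not reproducible for these events, and they may miss the 24-48 hour report and the individual SAE report to the IRB.

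The size cannot be found from the documents. The range of about 0.3 to 7.5 subjects per arm rests wholly on the assumed readmission rate and the assumed overlap with other criteria. The effect is confined to the SAE tabulation and the timing and route of reporting; the underlying events are still recorded.

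**What to change.** Add one criterion to Section 13.1.2: *requires unplanned inpatient hospitalisation, or prolongation of the index hospitalisation because of a documented untoward event (not length of stay alone)*. The closing condition is needed because the protocol defines no expected index stay against which to judge prolongation.

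Keep the exemption for planned admissions in Section 13.1.1. Apply the new criterion to every unplanned readmission within 30 days of surgery, whether found in the record or at the telephone call. The call alone should not be the trigger: it may fall before day 30, and an instruction to report every readmission mentioned in it would conflict with the planned-admission exemption.

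Before analysis, reconcile the 30-day readmission data with the SAE listing by cohort, so that each unplanned readmission has a matching SAE report.

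The cost is a short amendment, a few more SAE forms, one reconciliation step and a higher reported SAE count, which the report should attribute to the definition.
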